9.9.3.4. Unexpected Adverse Events

Adverse events that are not expected and not identified in the protocol or consent form. Adverse Events in this category will be reported.

Abnormal laboratory value

A laboratory abnormality should be documented as an adverse event if:

- The abnormality suggests a disease and/or organ toxicity, **OR**
- The abnormality is of a degree that requires active management; (e.g., specific treatment, more frequent follow-up assessments, further diagnostic investigation, etc.) **AND**
- The laboratory abnormality is not otherwise refuted by a repeat test to confirm the abnormality.

NOTE: Participants and their parent/legal guardian (s) will not be informed of any of the results collected and processed in the future for research purposes. These are research data only and not meant for the purpose of diagnostic evaluation. The results will not become part of the participant's medical record.

9.9.3.5. Unanticipated Problem Involving Risk to Participants or Others

Any incident, experience, or outcome that meets all of the following criteria:

- Unexpected (in terms of nature, severity, or frequency) given (a) the research procedures that are described in the protocol-related documents, such as the IRB-approved research protocol and informed consent document; and (b) the characteristics of the subject population being studied
- Related or possibly related to a participant's involvement in the research

- Suggests that the research places subjects or others at a greater risk of harm (including physical, psychological, economic, or social harm) related to the research than was previously known or recognized.

9.9.3.6. Serious Adverse Events (SAE)

Any event that is life threatening or fatal; results in significant or persistent disability; requires hospitalization or represents other significant hazards or potentially serious harm to research subjects or others, in the opinion of the investigators. The appropriate case report form must be completed for all events in this category according to the guidelines listed in the Manual of Procedures.

9.9.4. Adverse Event Reporting Period

The study period during which adverse events must be reported is normally defined as the period from the initiation of any study procedures to the end of the study follow-up. For this study, the study treatment follow-up is defined as the last scheduled visit.

9.9.5. Recording and Reporting Adverse Events

At each contact with the subject, the investigator must seek information on AEs by specific questioning and, as appropriate, by examination. Information on all adverse events should be recorded immediately in the source document, and also in the appropriate AE module of the case report form (CRF).

All adverse events occurring during the study period must be recorded. The clinical course of each event should be followed until resolution, stabilization, or until it has been determined that the study treatment or participation is not the cause. The following data will be recorded:

- Any event reported by the participant or parent/legal guardian, other than those expected and identified as detailed in the MOP will be immediately reported to the site PI.
- Signs and symptoms will be graded by the Unblinded Research Coordinator utilizing a 5-grade scale as listed in the manual of procedures.
- Each event will be assessed by the Principal Investigator (PI) for its relationship to study participation according to the guidelines listed in the Manual of Procedures.

9.9.6. Hospitalization, Prolonged Hospitalization or Surgery

Any adverse event that results in hospitalization (refer to manual of procedures for definition) surgery or prolonged hospitalization, should be documented and reported as a Serious Adverse Event (SAE) unless it is AT surgery occurring as a

treatment arm. Any condition responsible for surgery should be documented as an adverse event if the condition meets the criteria for an adverse event.

Neither the condition, hospitalization, prolonged hospitalization, nor surgery are reported as an adverse event if it occurred for a diagnostic or elective surgical procedures for a preexisting condition. Surgery should not be reported as an outcome of an adverse event if the purpose of the surgery was elective or diagnostic and the outcome was uneventful.

9.9.7. Follow Up on Adverse Events

The clinical investigator will follow every AE to a satisfactory outcome or stabilization of the event, even when this requires a time period beyond the scope of the study. The clinical investigator will record each AE outcome on the CRF according to the instructions outlined in the MOP. SAEs that are ongoing at the end of the study period must be followed to determine the final outcome. Any SAE that occurs after the study period and is considered to be possibly related to the study treatment or study participation should be recorded and reported immediately.

9.9.8. Post-Study Adverse Event Follow-Up

All unresolved adverse events should be followed until the events are resolved, the subject is lost to follow-up, or the adverse event is otherwise explained. At the last scheduled visit, the investigator should instruct each participant and parent/legal guardian (s) to report any subsequent event(s) that they believe may be related to participation in this study

9.9.9. Treatment Failure

This will be defined as a change in clinical status interpreted by the Medical Safety Monitor as requiring an immediate change to established clinical therapy for SDB. Operationally, potential treatment failures will be identified by the research coordinator based on interim telephone calls, emails and/or text messaging and research visits, or contacts initiated by the participant or their referring physician. Information will be submitted to the Medical Safety Monitor who will make an adjudication of the status of the participant and notify the PI who will arrange medical follow-up as indicated. Data will be subsequently reviewed by the DSMB. Note that, as the study will utilize an intent to treat paradigm, every effort will be made to continue the participant in the study, regardless of whether the participant receives clinical treatment or not.

Examples of treatment failures include worsening symptoms of SDB such as:

- 1) sleepiness interfering with schoolwork.
- 2) new academic or behavioral problems resulting in a recommendation for grade retention, special education, or counseling
- 3) placement on new medications for behavioral or emotional problems
- 4) recurrent bacterial tonsillitis defined as 3 or more episodes of streptococcal

culture positive infection occurring over a 3-month time interval. Children who have medical record documentation of 3 culture positive infections are asked to undergo a repeat throat culture after completion of the third course of antibiotics to exclude a chronic carrier state. If this test is not ordered for routine clinical purposes, it will be arranged by the study staff and paid for by the study.

Parent/legal guardian (s) who decide that they no longer want to wait 12 months for their child to be re-evaluated for AT surgery, but whose children do not meet any of the criteria for treatment failures, are not considered treatment failures. These children will be reevaluated by the ENT physician who initially evaluated them, unless they prefer to seek other medical consultation, and will be classified as crossovers.

9.9.10. Reporting Serious Adverse Events

The clinical site is responsible for reporting SAEs to the DCC within 48 hours of first knowledge of the event by creating an Adverse Event Report in the data management system (Slice) listing participant ID, description of the event and adverse event date. Creation of this initial report will automatically notify the DCC and provide summary data for the adverse event. SAEs will be reported to the Data Coordinating Center Project Manager, the Children's Hospital of Philadelphia IRB, the DSMB Chair, and the NHLBI Program Scientist within 7 days of its occurrence. The DCC will also provide follow up reports.

After the initial summary data are entered, the Research Coordinator and DCC will complete the full Adverse Event Report, including the following information:

- Study identifier (PATS)
- Study Center ID/Research Coordinator ID
- Participant Identification Number
- A description of the event in the form of a written narrative, including relevant medical history and/or co-morbidities
- Date of onset
- Date of resolution
- Study time point during which event occurred
- Randomization arm
- Whether study treatment was altered
- Description of actions taken by PATS staff, and follow-up required
- If the event is expected and non-mild, or unexpected

The research coordinator will provide further information on the AE in the form of a written narrative. This should include a copy of de-identified diagnostic tests or information that will assist in the understanding of the event. Significant new information on ongoing serious adverse events should be provided promptly to the DCC.

For all unexpected events and all events that are expected and serious the Medical Monitor will be notified and provided the Adverse Event Report. Using this report the Medical Monitor will complete an Adverse Event Adjudication form that will be available to the DCC and clinical site once completed, including the following information:

- Expectedness
- Relatedness
- Severity
- Whether the event constitutes a Treatment Failure
- If the event suggests a greater risk of harm than previously recognized
- Comments and recommendations for follow-up

In addition, the site must promptly report all SAEs and unexpected, related events to their IRB via written, dated notification in accordance with the IRB's reporting requirements. Copies of all such correspondence must be maintained in the clinical site's regulatory binder.

Upon notification from the clinical site, any serious adverse event that might reasonably be due to the study intervention will be reported to the monitoring bodies.

10. Medical Monitoring

It is the responsibility of the Principal Investigator to oversee the safety of the study at his/her site. *However, since the PI at each site is blinded to the treatment arm assignment, initial* screening of adverse events will be performed by the unblinded research coordinator. If the adverse event appears related to surgery, the coordinator will contact the otolaryngologic surgical co-investigator or other unblinded investigator at the site to ascertain the preliminary relationship to study participation, and coordinate follow up when applicable. The surgical co-investigator will contact the PI whenever he/she considers it medically necessary. Note that every site has a primary surgical co-investigator. If the adverse event appears not to be related to surgery, then the research coordinator will discuss the event with the PI or other unblinded co-investigator. When necessary, the DCC will notify the independent Medical Monitor for adjudication of all severe or related unexpected events for study purposes. The PI, IRB, Steering Committee, DSMB, and NIH Program Officer will be notified of all AEs, unanticipated problems, and Treatment Failures according to the reporting timeframe specified in the MOP. The PI's responsibility will include assuring that appropriate study data are communicated to the participant's family and physicians and that appropriate referrals or interventions are initiated.

Medical Monitoring will also include oversight by the Data Coordinating Center generating reports through regular assessment of the number and type of SAEs.

10.1. Medical Safety Monitor

A pediatrician who is board-certified in pediatric intensive care, pediatric pulmonology, and sleep medicine ([name], University of Rochester), unassociated with any clinical site, will serve as the independent Medical Safety Monitor. The Medical Safety Monitor will provide independent adjudication of unexpected and serious AEs and potential treatment failures. The Medical Safety Monitor will have access to randomization codes to make an informed decision about a particular participant. In addition to aggregate data, the Medical Safety Monitor will receive reports of all AEs that are:

- Expected and exceed thresholds
- Unexpected and Serious
- Unanticipated Problems that fit the reporting criteria

If a medical or psychological adverse event occurs that requires immediate intervention, it will be evaluated on an individual basis and study termination or recommendation regarding immediate AT surgery will be made. The Medical Safety Monitor will also evaluate both trends in AEs and Treatment Failures across the study and within each arm, as well as to confirm or refute the occurrence of specific treatment failures.

10.2. Serious Adverse Event and Unblinding of Treatment Arm

If there is an SAE, which is thought to be possibly or probably related to the coded intervention, the clinical site, when necessary for the safety of the participant, will unmask the treatment arm assignment. An explanation of the need for unblinding the treatment arm assignment must be provided to the DCC, who will disseminate the information to the various regulatory groups (DSMB, NIH) and external site PIs. Unblinding of the treatment arm assignment is anticipated to be an uncommon occurrence and is highly discouraged. An exception is made for any information identified that may pose acute health risks or would influence immediate treatment, in which case the PI will be notified immediately.

10.3. Management of Associated Adverse Events and Discontinuation of Treatment

The administration of the intervention may be discontinued at the subject's request or by the investigator, based on clinical judgment. If the subject is withdrawn from the study and participation terminated, the Study Stop CRF must be completed documenting the date study participation ended and identifying the reason. Parent/legal guardian (s) of participants who are discontinued will be instructed to report any AE experienced after treatment without delay.

10.4. Other Study Medical Monitoring and Reporting

10.4.1. Surgical Monitoring

Complications resulting from surgery will be documented at each site with use of an intra-operative data sheet and by reports obtained from the family during routine interim follow-up, supplemented by medical records, as appropriate. Major unanticipated adverse events and unanticipated problems that fit the reporting criteria will be reported (as required by institutional IRBs). The DCC will report complications from surgery to

the Surgical Quality Control Committee, the Independent Medical Monitor and to the DSMB and NHLBI. Periodically, these results will be tabulated and any significant deviations from reported national rates will be investigated. If any surgical complication is noted that exceeds expectation of usual care, or any site experiences excessive problems (as defined by the Surgical Quality Control Committee or the DSMB), [name], Director of the Surgical Quality Control Committee, will initiate an investigation. Actions may include ongoing monitoring, retraining, excluding the participation of specific surgeons, or excluding specific sites.

10.4.2. Severe OSA on PSG

10.4.3. Baseline

Any OSA is an exclusion for the study, so the participant with severe OSA will exit the study and the study team will facilitate appropriate clinical management.

10.4.4. Follow-Up

Data from follow-up PSGs will be available at a time when all 12 month follow up data have been collected to minimize influencing study outcomes, an approach that is standard for research data. However, an exception will occur for any information that meets the Urgent Medical Referral Criteria. Data will be shared earlier, as described above relative to baseline data.

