2.4.3. Follow-up Contacts

eAT arm only: AT surgery 1-4 weeks from randomization within Month 1

WWS arm only: ENT re-evaluation visit with 1-4 weeks after Endpoint Visit if indicated by 12-month PSG revealing obstructive sleep apnea (AHI ≥ 3.0 /hr. or obstructive apnea index > 1 /hr.) or parent reporting concerning symptoms.

Both groups:

- Monthly contact by telephone, email and/or text messaging , for health care utilization, medication, adverse event inquiries and to support study participation.
- Check In questionnaires and surveys will be completed bi-monthly, at months 2, 4, 6, 8, and 10.
- Interim remote visit at 6 months for caregiver questionnaires and neuro behavioral assessments, adverse event and health care utilization inquiry, and teacher forms of behavior rating scales.
 - Virginia will have in person child neurobehavior testing in addition to assessments above.
- Endpoint Visit at Month 12 for behavioral and performance testing; questionnaires; anthropometry, and BP measures. Behavioral rating scales mailed to teachers.
- Follow-up research PSG at Month 12
- Follow up questionnaires after participation ended to assess feasibility of conducting a study to evaluate long-term outcomes of mild SDB

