6.6. Potential Benefits to Participants and Others

There is prospect for direct benefit to participants, although it is possible that some or all participants will not receive direct benefits. Based on the nonrandomized smaller studies in children with MSDB, and the CHAT study on children with OSA beginning with an apnea hypopnea index as low as 2/hr, participants randomized to eAT may show

improvements in behavior, sleepiness and quality of life. It is also possible, based on adult data, that in children with MSDB, treatment will lower their cardiovascular risk profile²¹. Please see the rationale and Significance sections for a detailed description of the rationale for AT in improving behavior, sleepiness and quality of life in children with MSDB.

Participants randomized to WWSC may benefit by avoiding surgery if snoring and symptoms resolve without surgery or if the study shows that surgery does not improve behavioral outcomes.

In addition, all participants will receive information about healthy sleep habits for children. Children identified with obstructive sleep apnea during PSG may benefit from being screened for this study, but will ultimately be excluded from participation. Data collected for research purposes only (research PSGs, behavioral performance testing, behavioral rating scales and IgE level) will be made available to families, and the child's physicians after the study ends and may provide beneficial baseline information for future health concerns. Any data indicating a health risk will be made available to the child's physician as soon as those data are reviewed. The information obtained from this study will improve our understanding of the effects of MSDB on children's health, and will lead to better management, which is important as currently the management of MSDB varies widely across the country.

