8.2. Participants Randomized to Watchful Waiting with Supportive Care

After 12 months, children who did not get surgery who have a 12-month PSG showing obstructive sleep apnea (apnea hypopnea index >or =3.0 /hr or obstructive index > 1/hr) or whose parent reports ongoing symptoms/concerns will be referred back to ENT for further clinical management (such as adenotonsillectomy) as per standard clinical care.

9. Study Procedures

A study visit schedule is provided in Appendix A. Visit time points, study procedures and assessments are listed in the order in which they occur.

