9.9.2. Urgent Medical Referral Criteria

Conditions that will generate an Urgent Medical Referral Alert are those laboratory, physiological or behavioral findings that are believed to represent conditions that may require additional evaluation by the participant's health care providers in a timely manner. Because the participants in this study are pre-screened to be "otherwise healthy" children, most participants who meet Urgent Medical Referral Criteria are likely to be encountered at the time of their screening PSG and will no longer be eligible to participate and will exit the study to routine or urgent health care, as appropriate.

NOTE: At the baseline visit, one of the behavioral questions asks about suicidal ideation. A positive endorsement of that symptom will lead the study team to prompt assessment, deferred participation and possibly exclusion from the study, as appropriate for the participant's welfare. CBCL for children 6 years and older, the only measure that assesses for suicidal ideation, will be completed during an in person visit by the blinded RC only.

If the following conditions are identified during the course of the study, their occurrence will generate an Urgent Medical Referral by the Site PI who will communicate with the participant's parent or guardian, and with permission, contact the child's health care provider. Some of these conditions (abnormalities of blood pressure) will be noted as usually needing confirmation with repeat testing before clinical decision making.

- Stage 2 hypertension (> 99% for age and gender)
- PSG: Desaturation to < 90% for > 2% of total sleep time OAI >20/hr. or AHI > 30/hr.
- ABAS-3 score of <60
- Suicidal ideation

It should be noted that if any of these conditions occur after enrollment (i.e., not during a screening visit that disqualifies the child from enrolling in the study), these conditions will also be reported as Adverse Events.

An *Urgent Medical Referral Alert* should be completed and the site PI notified within 24 hours of first knowledge of the event.

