Aim 1: We will use the Wilcoxon rank-sum test to compare group changes in secondary behavior/performance measures including the GNG inhibitory control d'-prime and the average of the sustained attention d-prime and inhibitory control d-prime, SDB symptoms and quality of life endpoints over the 12-month study period. Generalized linear regression models will be used to model treatment effects adjusting for covariates. All outcomes other than PSG indices will be available at 6 months and 12 months and thereby can be analyzed using the mixed effects model outlined for the primary analysis, which does not assume a linear trajectory over time. For continuous outcomes which appear to have a linear trajectory over time, we will also estimate the rate of change in each treatment group and test the null hypothesis that the rates of change are equal for the eAT group and the WWS group using the following mixed effects model:

Let T denote time and $T=0, 1, 2$ refer to baseline, month 6 and month 12. Let X_3 denote the treatment indicator as before. The model will have each of the outcomes as response and include the main effects of T and the interaction effect of $T \times X_3$. The coefficient for $T \times X_3$ represents the treatment effect on linear trajectories.

Standard methods can be used to estimate this effect and test the null hypothesis of a zero effect.

For PSG indices (e.g., metrics of overnight hypoxemia, hypercapnia, sleep architecture, and breathing patterns) that are only available at baseline and 12 months, similar models can be used except that the variables corresponding to 6 months will be removed from the model. All participants enrolling in PATS entered the trial with an apnea-hypopnea index (AHI) under 3, i.e., without any evidence of obstructive sleep apnea syndrome (OSA). Estimating the proportion of participants who went on to develop OSA during the trial is thus of particular interest. We will also evaluate treatment effects on the proportion of participants with emergence of OSA (as defined by an $AHI \geq 3$) and 5 (indicating emergence of moderate or more severe OSA) at 12 months, and whether treatment effects differ by subgroups specified in Aim 3.

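### The month-12 sleep-study rules disagree on who is referred for OSA and when the result is released, and no explicit PSG-based referral covers an operated eAT child below the urgent-alert levels

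*Combined protocol and SAP*

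**What the plan says.** **Who is referred.** Section 2.4.3 ties the referral to the assigned arm: "WWS arm only: ENT re-evaluation visit with 1-4 weeks after Endpoint Visit if indicated by 12-month PSG revealing obstructive sleep apnea", or if the parent reports concerning symptoms. Section 9.7.6, the study description in Section 19 and the Appendix A table also confine it to WWSC. Note 2 of Appendix A says the WWSC group will be re-evaluated and omits the condition that the table row carries. Section 8.2 words the rule by treatment received: "After 12 months, children who did not get surgery who have a 12-month PSG showing obstructive sleep apnea", or whose parent has continuing concerns, go back to ENT. Section 2.1 says the same. OSA here means an AHI of at least 3/hr or an obstructive (apnea) index above 1/hr.

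**When the result is released.** Section 10.4.4 states that "Data from follow-up PSGs will be available at a time when all 12 month follow up data have been collected", and that "an exception will occur for any information that meets the Urgent Medical Referral Criteria". The PSG line of those criteria, in Section 9.9.2, is "PSG: Desaturation to < 90% for > 2% of total sleep time OAI >20/hr. or AHI > 30/hr". Section 6.6 makes research PSGs available to families and physicians once the study is over, but adds that "Any data indicating a health risk will be made available" to the child's physician once reviewed. It does not define a health risk.

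**What is measured.** Section 9.1.3 gives all participants the month-12 PSG, within 2 weeks either side of the daytime visit. Section 19 (Secondary Analyses, Aim 1) will evaluate treatment effects on the "proportion of participants with emergence of OSA", at AHI cut-offs of 3 and 5.

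**The concern.** The protocol treats an AHI of 3/hr or more at month 12 as OSA that calls for ENT review in one group of children, and states no equivalent route for another group with the same result. At entry, any child who fails the screening PSG is referred for clinical care (Sections 2.1 and 4.2). At month 12, the only scheduled PSG after randomization, an operated eAT child has no such explicit rule.

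The release rules add to this. A site holding a result above the referral threshold but below the urgent one is told in one place to wait and in another, arguably, to send it at once. Sites could therefore handle identical results differently. The issue is participant safety and consistent conduct; the primary analysis, alpha and power are not affected.

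**Working it through.** The plan gives no figure to reproduce, so the check sets the rules side by side.

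**1. Coverage of the explicit PSG-based referral**

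| Child | By arm (2.4.3, 9.7.6, Section 19, Appendix A) | By surgery received (2.1, 8.2) |
|---|---|---|
| WWSC, not operated | covered | covered |
| WWSC, operated during the year | covered | not covered |
| eAT, not operated | not covered | covered by the wording of 2.1 (8.2 stands under the WWSC heading) |
| eAT, operated | not covered | not covered |

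The second row is not hypothetical: Section 9.9.9 expects crossovers.

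**2. The band between referral and alert**

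Referral level: AHI ≥ 3 or OAI > 1. Urgent level, reading the Section 9.9.2 line as three alternatives: AHI > 30, or OAI > 20, or saturation below 90% for more than 2% of sleep time. A result is in the band if it meets the first and none of the second.

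| AHI | OAI | % of sleep time < 90% | Referral level | Urgent | In band |
|---|---|---|---|---|---|
| 2.9 | 0.5 | 0 | no | no | no |
| 3 | 0.5 | 0 | yes | no | yes |
| 10 | 4 | 0.5 | yes | no | yes |
| 30 | 20 | 2 | yes | no | yes |
| 30.1 | 5 | 0 | yes | yes | no |
| 12 | 3 | 2.1 | yes | yes | no |

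The last row shows that AHI and OAI alone do not define the band.

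**3. Release of a result in the band**

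Take AHI 10, OAI 4, 0.5% of sleep time below 90%. Section 10.4.4 says hold, because no urgent criterion is met. Section 6.6 says after the study if the result is not a health risk, and once reviewed if it is. Since the protocol sends this value to ENT in unoperated WWSC children, the second reading is reasonable, and it conflicts with the hold.

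**4. Fit with the ENT window**

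Set the endpoint daytime visit as day 0. The PSG falls on day −14 to +14 (9.1.3) and the ENT visit on day 7 to 28 (2.4.3).

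- Hold read per child, counting only the visit and the PSG: earliest release = max(0, PSG day), so day 0 to 14. Days left in the window: 28 − 0 = 28 down to 28 − 14 = 14. The rules are compatible.
- PSG on day +14: the window opened 14 − 7 = 7 days before the PSG took place, but 14 days remain.
- Teacher forms counted as 12-month data: they are first chased after 2 weeks and have no closing date (9.4), so release could pass day 28.
- Hold, or end of study, read trial-wide: the PSG-based visit cannot be met for most children.

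These are best-case figures, since no completion time for scoring and reporting the follow-up PSG is stated.

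**The case against.** The strongest reply is that the arm restriction has a purpose. Appendix A labels the visit as re-evaluation for surgery, and Sections 2.1 and 8.2 give adenotonsillectomy as the example of further management. It is the deferred-treatment pathway, and operated children have already had that surgery. Other provisions reach both arms: the urgent alert (9.1.7, 9.9.2), the health-risk sentence (6.6), the investigator's duty to see that data are communicated and referrals made (Section 10), and treatment-failure review (9.8). A PSG manual that is not part of these documents may say more.

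This explains the restriction but does not close the gap. Below the urgent levels, the general provisions carry no PSG threshold. Section 10 also says that the site investigator is blinded to arm, and the unblinded coordinator's listed month-12 scheduling task is the WWSC re-evaluation (2.3). The treatment-failure examples in 9.9.9 rest on symptoms and clinical events.

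Several stronger readings are tempting but not supported:

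- *No referral rule covers any eAT child.* Section 2.1 as worded covers an eAT child who was not operated on.
- *Every AHI from 3 to 30 escapes an alert.* The desaturation criterion can trigger one.
- *The hold flatly contradicts the 1-to-4-week visit.* Read per child, both can be met. Parent-reported concerns can also prompt re-evaluation without a PSG result (2.4.3, Section 19).
- *OSA is left over after surgery.* OSA is excluded at entry (10.4.3), so only new OSA is supported.
- *Families are never told research results.* The sentence in 9.9.3.4 stands under laboratory abnormalities and concerns future processing; Section 6.6 does release PSGs.

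**Conclusion.** The concern holds in three limited respects.

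1. An operated eAT child in the band has protocol-defined OSA and no explicit PSG-based referral.
2. A WWSC child who crossed over to surgery is covered by one set of rules and not the other.
3. For results in the band, Sections 6.6 and 10.4.4 are unreconciled on release, and neither says whether its timing is per child or trial-wide.

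Against the ENT window, the hold is an ambiguity that becomes a conflict only on a trial-wide reading or if late items count. For unoperated WWSC children only this release question applies, because the referral rule covers them.

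The band is AHI ≥ 3 or OAI > 1, with AHI ≤ 30, OAI ≤ 20 and saturation below 90% for no more than 2% of sleep time. How many children fall in it is unknown, as the documents give no rate of new OSA. The conclusion assumes that the unseen manuals do not already settle the matter. It takes no position on which referral or release rule is right.

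**What to change.** Reconcile Sections 2.1, 2.4.3, 6.6, 8.2, 9.7.6 and 10.4.4, the study description in Section 19, and Appendix A including note 2. One consistent text should state:

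- which children the month-12 OSA pathway covers, naming operated eAT children and WWSC crossovers;
- whether WWSC re-evaluation is conditional, so that note 2 agrees with the table row;
- whether the hold in 10.4.4 is per child or trial-wide, which items count as 12-month data, and when the hold ends relative to the 1-to-4-week window;
- how the hold relates to the health-risk sentence in 6.6.

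The threshold, the release timing and the clinical action are for the investigators to decide.

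The cost is protocol wording. Every child already has the PSG, it is centrally scored, and a route from the Reading Center to the site exists for alerts. The small downside is some additional result notices for sites to handle.
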